Study Protocol

Comparison Between the Axillary Bilateral-breast Approach (ABBA) and Bilateral Axillo-breast Approach (BABA) for Robotic Thyroidectomy (NCT02768753) April 30,2017

Objective

To compare the therapeuic effcts between the axillary bilateral-breast approach (ABBA) and bilateral axillo-breast approach (BABA) for robotic thyroidectom. To explore the efficacy, safety, cosmetic results and clinical value by the two approaches

Criteria

Inclusion Criteria: The initial surgery;preoperative needle aspiration biopsy of thyroid cancer, and the diameter of no more than 1cm, no lateral neck lymph node metastasis;the tumor is confined to the thyroid membrane, not invading trachea and recurrent laryngeal nerve;intraoperative frozen section diagnosis of thyroid cancer;the patient informed consent.

Exclusion Criteria : High-frequency ultrasound preoperative tumor diameter greater than 1cm, or lateral neck lymph node metastasis in patients;there had been a history of thyroid surgery or neck radiation therapy;pregnant or lactating women;with severe Hashimoto's thyroiditis, thyroid volume greater than II°;coagulation disorders,hyperthyroidism or hypothyroidism patients;sternal goiter.

Methods

All patients were dived into two groups randomly. According to the standard of surgey, the 60 patients who have been diagnosed with thyroid cancer are numbered. The random number is even assigned ABBA group(n = 30) and the random number is odd assigned BABA (n = 30). All patients were operated on by the same surgical team through the da Vinci robotic surgical system use method of circular mobilization. After the operation, the number of resected lymph nodes, intraoperative blood loss, postoperative pain scores 24h, catheterization time, the time of drainage, Swallowing Evaluation , Subjective Voice , operative time, postoperative hospital stay, cosmetic results satisfaction, recurrent laryngeal nerve injury and hypoparathyroidism and other related complications were compared between groups. The patients were

followed up for 3~22 months.

Data management and statistical analysis:

SPSS 22.0.0 software was used for statistics. The measurement data were used to describe the average number of standard deviation; the ratio / rate of counting data was calculated; the measured data between the two groups were compared with the paired t test; the rate of the two groups was compared with the chi square test. The difference was statistically significant in p<0.05.

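### Measured outcomes in two separately randomised groups are to be compared with a paired t test, although the plan defines no pairs

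*Combined protocol and SAP*

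**What the plan says.** The Methods section describes a parallel-group design: "All patients were dived into two groups randomly". The patients are numbered individually ("the 60 patients who have been diagnosed with thyroid cancer are numbered"), and parity decides the group: "The random number is even assigned ABBA group(n = 30) and the random number is odd assigned BABA (n = 30"). Outcomes such as node count, blood loss, operative time and hospital stay are then compared between the groups.

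Under Data management and statistical analysis, the only between-group test for measured data is given as "the measured data between the two groups were compared with the paired t test". For counted data, "the rate of the two groups was compared with the chi square test". The decision rule is "The difference was statistically significant in p<0.05". No confidence interval is specified.

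**The concern.** A paired t test analyses differences within pairs, so each observation needs a defined partner. Here the two groups contain different people, and nothing links an ABBA patient to a BABA patient. The test is explicitly applied between the groups, which rules out a before-and-after comparison within one group. In the same sentence, the chi-square test for rates treats the same two groups as independent.

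Without a rule, the software pairs patients by their position in the file. Two analysts holding the same 60 records in different orders could report different p-values for the same outcome and, near 0.05, opposite conclusions. The plan's only decision criterion is p<0.05, so nothing else in it would reveal the problem. Chi-square p-values are not affected.

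**Working it through.** **Inputs.** From the plan: n = 30 per group, 60 different patients, significance at p<0.05. Assumed: two-sided testing (sides are not stated), normal-shaped data, equal SDs. The plan gives no effect size, SD or power, so it has no figure on this point to reproduce. Differences in SD units below are assumptions.

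**1. What pairing changes.** With complete 30:30 data, the group means, SDs and mean difference are the same under any pairing. The standard error is not:

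- Independent: SE = s·√(2/30), df = 30 + 30 − 2 = 58, critical t = 2.002.
- Paired: SE = s·√(2(1 − r)/30), df = 30 − 1 = 29, critical t = 2.045.

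Here r is the correlation that the row order happens to produce, so t(paired) = t(independent)/√(1 − r).

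**2. How far r can move the p-value.** Under random ordering, r has mean 0 and SD 1/√29 = 0.186, so about 95% of orders give r within ±1.96 × 0.186 = ±0.36. Take an outcome with independent-samples p = 0.050 (t = 2.002):

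- r = −0.36: p = 0.097
- r = 0: p = 0.055
- r = +0.36: p = 0.018

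The paired test is significant when 2.002/√(1 − r) > 2.045, that is, when r > 1 − (2.002/2.045)² ≈ 0.042. That is 0.042/0.186 ≈ 0.23 SD above zero, which a normal approximation puts at about 41% of orders.

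**3. Simulation of the same point.** 20,000 random re-pairings of a fixed data set gave:

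| Independent-samples p | Central 95% of paired p | Share of orders with paired p<0.05 |
|---|---|---|
| 0.01 | 0.002 to 0.030 | about 100% |
| 0.03 | 0.009 to 0.067 | 84% |
| 0.05 | 0.018 to 0.097 | 41–42% |
| 0.07 | not tabulated | 16% |
| 0.10 | 0.045 to 0.163 | 4% |
| 0.20 | 0.116 to 0.275 | 0.01% |

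**4. Disagreement over repeated trials.** With pairing blind to outcome (200,000 simulated trials per setting), the two tests disagree on significance in 1.7% of trials with no true difference. They disagree in 4.2% at 0.3 SD, 6.0% at 0.5 SD and 3.6% at 0.8 SD.

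**5. Type I error and power.** With outcome-blind pairing, type I error is about 5% for either test. Power uses the noncentral t with noncentrality d·√(30/2):

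- d = 0.5 (noncentrality 0.5 × √15 = 1.94): 47.8% independent, 46.5% paired.
- d = 0.8 (noncentrality 0.8 × √15 = 3.10): 86.1% independent, 85.0% paired.

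This holds only if row order is unrelated to the outcome. If both groups were sorted by the outcome before pairing, type I error would be about 67%; sorted in opposite directions, about 0.6%. These are extreme cases, but the plan excludes neither.

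**6. Unequal groups or missing values (conditional).** The paired test drops any patient without a complete partner. The plan states 30:30 but no mechanism that forces it. If each number were drawn freely, an exact 30:30 split would have probability C(60,30)/2⁶⁰ = 10.3%. At an assumed 32:28 split the paired test omits 60 − 2 × 28 = 4 patients; at 36:24 it omits 60 − 2 × 24 = 12.

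**The case against.** The strongest objection is that 'paired' is a slip of language. The document contains many, the sentence itself says the comparison is between two groups, and nobody is paired. On that reading an ordinary t test was intended and the order dependence never arises. This is plausible and cannot be settled from the document. It does not remove the point: no other test is named for measured data, and the wording needs the same correction either way.

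The second objection concerns size. The effect estimates are unchanged, type I error is near nominal and the power loss is trivial. The two tests disagree in only a few percent of trials, and the 41–42% figure belongs to an outcome sitting exactly at 0.050. All of this is correct, and the point should not be argued on power or false positives. What stands is that the specified test is wrong for the design and that its p-value is not determined by the data.

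Third, the unequal-group figures depend on arms departing from the stated 30:30. The conclusion does not rely on them. Finally, any independent-samples t test would cure the defect, so Welch is a preference. With equal group sizes and equal SDs it gives the same t and the same 58 df as the pooled test used in the working.

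**Conclusion.** The concern holds; the analysis rule is wrong as written and must be corrected. The plan assigns different patients to each arm, defines no pairs, and names a paired test as its only between-group comparison of measured data. For an outcome near the threshold, the row order alone can decide significance: at an independent-samples p of 0.050, the central 95% of paired p-values runs from 0.018 to 0.097. At 0.01 or 0.20 the conclusion almost never changes. These percentages assume two-sided testing, normal-shaped data, equal SDs and complete 30:30 data, so they illustrate the problem and do not estimate its effect in this trial. The mismatch between test and design needs none of those assumptions. Whether the paired test was actually run cannot be determined from the document.

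**What to change.** In Data management and statistical analysis, replace the paired t test with an independent-samples t test (Welch), and report each between-group mean difference with its 95% CI. Where a measured outcome is ordinal or clearly skewed, a rank test for independent groups is a compatible choice if named in advance. If pairs really were formed, the plan must instead state the matching rule and how patients were randomised within pairs.

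The cost is one sentence and no new data. The text is written partly in the past tense, so if the paired test has already been run, each measured outcome needs one re-run with the independent-samples test and the reported p-values should be replaced.

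### Complications in arms of 30 are compared only by chi-square at p<0.05, without a risk difference or interval; by score-type intervals any non-significant result leaves at least about 11 points open

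*Combined protocol and SAP*

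**What the plan says.** The Objective section makes safety one of the aims: "To explore the efficacy, safety, cosmetic results and clinical value by the two approaches". The Methods section allocates 60 patients, 30 to each approach, and closes its list of outcomes with the safety items: "recurrent laryngeal nerve injury and hypoparathyroidism and other related complications were compared between groups".

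The section on data management and statistical analysis treats all count outcomes alike. As description, "the ratio / rate of counting data was calculated". As comparison, "the rate of the two groups was compared with the chi square test". The decision rule is "The difference was statistically significant in p<0.05".

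The document gives no between-arm effect measure, no confidence interval, no margin and no expected complication rates. It does not say which form of the chi-square test is meant, or what to do when counts are small.

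**The concern.** A p-value above 0.05 does not say how large a difference remains possible, and with 30 patients per arm a large one does. If complications are uncommon, the plan's rule will usually return either no significant difference or nothing computable. The plan offers nothing beside that result to show its limits. Since safety is an aim, the trial should be able to say which differences in complication risk its data exclude and which they do not. Per-arm rates and a p-value do not say that directly.

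**Working it through.** The plan has no power or precision calculation to reproduce. The inputs it does give are n = 30 per arm (Methods) and a 0.05 threshold (statistical analysis section). Write a and b for the event counts in the two arms, and S = a + b.

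**1. When can chi-square reject?** With equal arms of 30:

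- Uncorrected: X² = 60(a − b)² / [S(60 − S)]
- Yates: X² = 60(|a − b| − 1)² / [S(60 − S)]
- Critical value: 3.841

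For a given S the most extreme split is S vs 0, where the uncorrected statistic becomes 60S/(60 − S).

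- S = 0: the denominator is zero, so there is no test.
- S = 3: 180/57 = 3.158, p = 0.076. Yates: 60 × 4/171 = 1.404, p = 0.236.
- S = 4: 240/56 = 4.286, p = 0.038. Yates p = 0.12.

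So neither form can reject with 3 or fewer events. Fisher's test cannot either (3 vs 0: p = 0.237).

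**2. What does a non-significant table leave open?** The Newcombe 95% interval combines the Wilson limits (l, u) of each arm:

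- Lower: d − √[(p₁ − l₁)² + (u₂ − p₂)²]
- Upper: d + √[(u₁ − p₁)² + (p₂ − l₂)²]

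At 0 vs 0 the Wilson upper limit is z²/(n + z²) = 3.841/33.841 = 0.1135, so the interval is ±11.4 points. At 3 vs 0 the Wilson limits are 0.0346 to 0.2562 and 0 to 0.1135. The lower limit is 0.100 − √(0.0654² + 0.1135²) = −0.031, and the upper limit is 0.100 + 0.1562 = 0.256.

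| Events | Uncorrected p | Newcombe 95% interval (points) |
|---|---|---|
| 0 vs 0 | not computable | −11.4 to +11.4 |
| 1 vs 0 | 0.31 | −8.3 to +16.7 |
| 1 vs 1 | 1.00 | −13.6 to +13.6 |
| 2 vs 0 | 0.15 | −5.7 to +21.3 |
| 3 vs 0 | 0.076 | −3.1 to +25.6 |
| 4 vs 0 | 0.038 | −0.6 to +29.7 |

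There are 31 × 31 = 961 possible tables. The uncorrected test fails to reject, or cannot be computed, in 361. Taking the limit further from zero in each of these, the smallest value is 11.4 points. It is reached at 0 vs 0 and at its mirror image, 30 vs 30. At every other such table the limit is at least 13.6 points. The floor is the same with Yates' correction. By Miettinen-Nurminen it is 11.5 points.

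**3. How often are there 3 or fewer events?** The plan gives no rates, so these are assumptions. With a common rate p, S is binomial(60, p).

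| Assumed rate, both arms | 3 or fewer events | No events |
|---|---|---|
| 2% | 97% | 30% |
| 5% | 65% | 5% |
| 10% | 14% | 0.2% |
| 15% | 1.5% | below 0.1% |

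**4. Does the form of the test matter?** Among splits with up to 30 events, 14 are significant uncorrected but not by Yates or Fisher. They run from 4-0 and 5-0 up to 19-11. For example, 8 vs 2 gives 0.038 uncorrected, 0.083 by Yates and 0.080 by Fisher.

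**The case against.** The strongest reply is that the plan makes no false statement. It sets out to explore safety, claims neither equivalence nor non-inferiority, and nowhere says that p>0.05 means equal safety. A reader might infer that the plan intends to declare the approaches equally safe; the text does not support that. The plan also calculates per-arm rates, so anyone with the denominators can work out an interval afterwards. This stands, and it limits the point to one of reporting and method.

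Other stronger readings also fail.

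- That 11 points is left open whatever interval is used. The floor belongs to score-type intervals. At 0 vs 0, Agresti-Caffo gives ±8.5 points and Wald gives 0 to 0.
- That 361 of 961 is a probability. It is an unweighted count of tables.
- That the test will usually be unable to reject. This holds at assumed rates of 2% or 5%, but not at 10% or above.
- That uncorrected chi-square inflates false positives materially. Its maximum size at 30 per arm is 5.5%.

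Two practical objections also stand. Patients were "followed up for 3~22 months", and the plan gives no definition or time window for nerve injury or hypoparathyroidism; an interval does not cure that. And the Methods are written in the past tense, so the change may come too late to count as pre-specified.

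**Conclusion.** The point holds as a modest, inexpensive improvement. The comparison of complications rests on a chi-square p-value alone. That p-value does not exist at 0 vs 0, and it cannot fall below 0.05 with 3 or fewer events, corrected or not. No non-significant table at 30 per arm excludes a difference of about 11 points in both directions by a Newcombe or Miettinen-Nurminen interval, and most leave far more open.

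The 11-point floor needs no assumed event rate. It does rest on a two-sided 95% score-type interval and on all 30 patients per arm being evaluable. How often the test is powerless to reject rests wholly on assumed rates.

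**What to change.** For each complication, report events out of the evaluable patients in each arm, and the risk difference with a 95% interval, as the main safety summary. Name a small-sample method, for example Newcombe; Wald will not do, because it has zero width at 0 vs 0. State that p>0.05 will not be read as equal safety. As a secondary change, name one form of chi-square, or an exact test, for all tables; which one is for the sponsor to choose.

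The cost is SAP wording, with no new patients or data. Newcombe limits follow by formula from the two counts if the named software does not supply them. There are four downsides.

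- The interval adds no power.
- Newcombe is somewhat conservative when events are rare: coverage is 95% to 100%, mean 97%, for rates of 0.5% to 20%.
- Among splits with up to 30 events it disagrees with the uncorrected test at 4-0 and 6-1, where p<0.05 but the interval includes zero. The SAP should say that the interval leads for safety.
- If the data are already collected, this is a change in reporting and should be labelled as such.

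### Does leaving the version of the chi-square test unnamed weaken the comparison of rates?

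*Combined protocol and SAP*

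**What the plan says.** The section on data management and statistical analysis describes rates and then tests them: "the ratio / rate of counting data was calculated", and "the rate of the two groups was compared with the chi square test". The threshold is "The difference was statistically significant in p<0.05", and the only software detail is "SPSS 22.0.0 software was used for statistics". The Methods section shows which outcomes this covers; they include safety outcomes: "recurrent laryngeal nerve injury and hypoparathyroidism and other related complications were compared between groups". It also gives the arm sizes: "The random number is even assigned ABBA group(n = 30) and the random number is odd assigned BABA (n = 30").

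No version of the test is named. There is no rule for small expected counts and no statement on outcomes with no events. Sidedness, expected event rates and power are not given either.

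**The concern.** Complications may be uncommon, and the arms are small. In sparse two-by-two tables the versions of the chi-square test differ most, so an analyst who sees the counts before settling the version could in principle choose the verdict. Four complications against none gives p = 0.038 by Pearson and 0.121 by Yates. Three against none gives 0.076 by Pearson and 0.038 by likelihood ratio. Naming the software does not name the statistic.

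At stake would be the reported significance of a difference in nerve injury, hypoparathyroidism or another complication, and so part of the safety comparison of the two approaches. A secondary worry is that an outcome with no events in either arm has no chi-square statistic at all.

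**Working it through.** The plan states no power, effect size or p-value for rates, so there is no figure of its own to reproduce beyond 30 + 30 = 60, which is consistent.

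**Inputs.** From the plan: 30 patients per arm and a threshold of 0.05. Assumed: a two-sided test, and every event rate used below.

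**Formulas.** With a and b events in arms of 30, s = a + b, N = 60 and D = |a(30 − b) − b(30 − a)|:

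- Pearson: X² = N·D² / (30·30·s·(60 − s))
- Yates: the same with D replaced by D − N/2 = D − 30 (zero if negative)
- Likelihood ratio: G² = 2·Σ O·ln(O/E) over the four cells

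Each is referred to chi-square on 1 degree of freedom (critical value 3.84).

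**Two tables by hand.**

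- 4 against 0: D = 4·30 − 0·26 = 120, and the denominator is 900·4·56 = 201,600 once N is kept on top. X² = 60·120²/201,600 = 4.29, p = 0.038. Yates = 60·90²/201,600 = 2.41, p = 0.121.
- 3 against 0: D = 90. X² = 60·90²/(900·3·57) = 3.16, p = 0.076. G² = 2[3·ln(3/1.5) + 27·ln(27/28.5) + 30·ln(30/28.5)] = 4.32, p = 0.038.

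**All tables.** There are 31 × 31 = 961 pairs of counts; the two with no events or all events have no statistic and count as not significant.

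| Comparison at p < 0.05 | Tables |
|---|---|
| Significant by Pearson | 600 |
| Significant by Yates | 546 |
| Pearson significant, Yates not | 54 |
| Yates significant, Pearson not | 0 |
| Likelihood ratio significant, Pearson not | 12 |
| Pearson significant, likelihood ratio not | 0 |

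Fisher's exact test gives the same verdict as Yates in every table. Of the 54 discordant tables, 38 have all expected counts of at least 5, so they are not only the sparse ones (12 against 5, for instance: Pearson 0.045, Yates 0.086).

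**Type I error at equal true rates** (binomial probabilities summed over the significant tables):

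| Assumed rate in both arms | Pearson | Yates | Likelihood ratio |
|---|---|---|---|
| 2% | 0.3% | 0.003% | 2.4% |
| 5% | 2.8% | 0.15% | 8.3% |
| 10% | 5.4% | 0.9% | 7.5% |
| 20% | 4.9% | 2.2% | 6.1% |
| 50% | 5.2% | 2.7% | 5.2% |

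Pearson's maximum is 5.54%, near a rate of 11.6%. The likelihood-ratio maximum is 8.9%, near 6.5%.

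**How often the version would matter.** Pearson and Yates disagree with probability 0.3% at an equal rate of 2%, 2.7% at 5%, 4.5% at 10% and 2.7% at 20%. If the rates truly differ it is more: 17.5% for 2% against 10%, and 28.9% for 2% against 20%, where power is 69% by Pearson and 41% by Yates. Pearson and likelihood ratio disagree with probability 5.5% at an equal rate of 5%.

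**No events.** The chance of none in 60 patients is (1 − rate)^60: 0.99^60 = 55%, 0.98^60 = 30%, 0.95^60 = 4.6%. The only possible report is then zero in each arm; no decision is open.

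**The case for a change.** The best case for a change is that the version is undetermined on paper and the verdict can move either way: Yates or Fisher can remove significance, and likelihood ratio can add it with a type I error of up to 8.9%. It would therefore be wrong to call the ambiguity harmless on the ground that it can only cost significance. Naming the version would take a few words and lose no power. When true rates differ clearly, the choice between Pearson and Yates could decide the verdict in more than a quarter of trials.

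The arithmetic stands. What does not follow is a flaw in the plan. The worry needs the analyst to set aside the plain meaning of an unqualified chi-square test and pick a named variant that the plan never mentions. An analyst who carries out the sentence as written gets a valid test, and the suggested wording would specify that very test. Confidence intervals per arm, a score interval for the risk difference or a sentence on outcomes with no events would be useful in a report, but they are reporting preferences and alter no decision under the plan.

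One limit remains. The 5.5% ceiling belongs to arms of exactly 30. If the arms ended unequal, Pearson's maximum would be 5.6% at 28/32, 5.8% at 27/33 and 6.5% at 25/35 (assumed splits). These excesses are small and would remain if Pearson were named.

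**Conclusion.** The plan does leave the chi-square version unnamed, but this is missing detail that an analyst fills sensibly, and it calls for no change. The plain reading, uncorrected Pearson, holds its level at 30 per arm to within about half a percentage point (maximum 5.54%). The other versions would change the verdict in 54 tables (Yates or Fisher, losing significance) or 12 tables (likelihood ratio, gaining it) out of 961. Counts reported per arm would let a reader recover any of them.

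This rests on a two-sided test, on arms of 30 as planned, and on the ordinary meaning of an unqualified chi-square test. The frequencies of disagreement rest on assumed event rates, since the plan gives none; the table counts do not.
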